## **Study Protocol: Evaluation of the Effects of Virtual Reality Learning Environment on Nursing Student Non-technical Skills Development: A Quasi-Experimental Study**

### **Background and information**

A Virtual Reality (VR) Ward Training System with a virtual environment was installed in the School of Nursing, The Hong Kong Polytechnic University. The objective of the VR system is to enhance students' situation awareness and communication skills. A complete set of 3D rendering scenes are created for three learning modules. In addition, there is real-time animation interacting with controllers.

Virtual Hospital is a laboratory mimicking a real hospital in a virtual platform to allow students to attend their clinical practice. The VR technology can be applied to simulate a clinical environment for students to experience as if they were learning in a hospital while they are in fact on campus. The equipment will allow stages of learning through beginners and graduating students.

Currently, students will have simulation sessions as the usual teaching method on the clinical reasoning subject to train their clinical communication and situation awareness skills. The VR ward training system will be used to improve students' learning experience.

The proposed research study investigates whether the VR teaching pedagogy will have added value in developing students' situation awareness, communication skills, and self-confidence in learning.

Virtual reality (VR) uses a computer system to simulate real-life events, and the users can interact with the virtual environment (Alrehaili & Osman, 2019). The main characteristics of the

VR applications included immersion, interaction and imagination (Burdea & Coffiet, 2003). VR has been widely studied in education and has shown promising results, especially in improving

learner motivation, engagement and attention (Virvou et al., 2005). VR environments merging

with game-based approaches are more commonly used in recent years. Merchant et al. (2014)

conducted a meta-analysis on the effectiveness of VR technology in three areas: virtual worlds, Document Date: January 1, 2022

games and simulation environments. The VR context improves knowledge acquisition in the game's environment among these three areas. The study also found that the users who played the games had a higher retention level. Alrehaili & Osman (2019) also revealed that VR serious games could improve students' knowledge retention and motivation in learning.

## **Study Aims**

This study evaluates the benefits of the Virtual Reality ward training system. It aims to explore the impact of the VR system on students' situation awareness, communication skills and self-confidence in learning.

The primary question is: *Does Virtual Reality improve student's learning outcome (1) situation awareness; (2) communication skills; and (3) self-confidence in learning?*

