## **Methodology**

### Study design

The study employs a quasi-experimental, pretest-posttest non-equivalent waitlist control group design. It is unethical to forbid a group of students from receiving a potential beneficial educational intervention for their learning purposes. In contrast, a waitlist design is appropriate to address the concern. The control group will not receive the intervention until after data has been collected. A pretest-posttest method will be used because of possible differences between the two groups.

Two intact groups, which cannot be randomly assigned, serve as the control and intervention groups. The intervention group will be having the VR training, whereas the control group will not until the study is completed.

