## Participants

Students studying Bachelor of Science in Nursing who have completed the subject “Clinical reasoning and decision making in action part 1” are eligible to participate in the study (n=200). The researcher accepts a margin of error at 5%, confidence interval at 95% and standard deviation of 0.5. By using the Z-score formula (*Necessary Sample Size = (Z-score)2 \* StdDev\*(1-StdDev) / (margin of error)2*), the sample size should be  $N = 132$ . To avoid dropout and attrition from the participants, the researcher will recruit 150 samples to participate in the study.

Convenience sampling will be adopted to recruit subjects. Participants will be assigned to two study groups, the control and the experimental group. The Control group will have usual teaching activities (simulation), whereas the participants of the intervention group, will have VR sessions.

[figure not shown]

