## Instrumentation

The study aims to assess students' situation awareness, communication skills and self-confidence in learning. Two validated instruments are used to measure the dependent variables.

The first and second dependent variables, student's situation awareness and communication skills, will be tested using the revised "NOn-TECHnical skills (NOTECHS)" scale (Sevidalis et al., 2008). The scale is a widely accepted instrument to measure health care workers non-technical skills. The scale consists of 22 items with five subscales, including communication and interaction, situation awareness and vigilance, cooperation and team skills, leadership and managerial skills and decision making. The correlation coefficients for the five subscales reported range from ( $\alpha$  .77 - .87), demonstrated promising evidence of internal consistency of all subscales.

The third dependent variable, student's self-confidence in learning, will be tested using the "Student satisfaction and self-confidence in Learning" inventory (National League for Nursing, 2005). A total of 13 items assess the attitudes toward satisfaction with instruction and self-confidence in learning in simulation. A "satisfaction with instruction" subscale contains five items measuring satisfaction with teaching methods, diversity of learning materials, facilitation, motivation, and overall suitability of simulation. A "self-confidence with learning" subscale contains eight items measuring self-confidence in content mastery, content necessity, skills development, available resources, and knowledge of how to obtain help to solve clinical problems in simulation. Participants indicate their personal feelings about a statement that describes their attitudes or beliefs for each item. Response options include 1) strongly disagree, 2) disagree, 3) undecided, 4) agree, and 5) strongly agree according to Likert-style scale. Cronbach's alpha was reported as 0.94 for the satisfaction subscale and 0.87 for the self-

confidence subscale (Jeffries and Rizzolo, 2006). Scores are calculated by summing responses; higher scores indicate more satisfaction and more self-confidence, respectively.

Apart from the instruments, students' demographic data will be collected, including the prior experience in VR use to see whether previous VR experiences will affect the result.

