### Data Analysis

The quantitative data will be analyzed using IBM SPSS for Windows version 26. Frequency and/or mean will be used to describe the demographic data. Descriptive data such as mean and median will describe the prevalence of attitudes and self-confidence, level of situation awareness and communication skills. Mann-Whitney U test will be used to examine the changes in mean scores of variables (attitudes and self-confidence, level of situation awareness and communication skills) between the control and experimental groups. A content analysis of the qualitative data will be conducted for the data collected from the debriefing session.

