## Conclusion

Non-technical skills in the healthcare industry are vital to maintaining patient safety and preventing errors. The effectiveness of the technology-assisted teaching pedagogy is well studied. However, the use of VR to develop students' non-technical skills in healthcare education field is not common. The proposed study investigates the effectiveness of the VR training system on situation awareness, communication skills and self-confidence in learning development in university nursing students.

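### Do three unranked primary outcomes with no stated success rule call for a multiplicity adjustment?

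*Combined protocol and SAP*

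**What the plan says.** The Study Aims section asks whether VR improves "learning outcome (1) situation awareness; (2) communication skills; and (3) self-confidence in learning". The three are numbered but not ranked. The Instrumentation section calls them the first, second and third dependent variables. It takes the first two from subscales of the revised NOTECHS scale and the third from a 13-item inventory with a 5-item satisfaction subscale and a self-confidence one ("subscale contains eight items measuring self-confidence in content mastery").

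The Data Analysis section applies a Mann-Whitney U test to the "variables (attitudes and self-confidence, level of situation awareness and communication skills) between the control and experimental groups". It gives no significance level, sidedness, testing order or adjustment, and does not say how the three results combine.

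The only 5% and 95% figures are in the Participants section: "The researcher accepts a margin of error at 5%, confidence interval at 95% and standard deviation of 0.5". On purpose, the Study Aims section says "It aims to explore the impact of the VR system", and the Conclusion says "The proposed study investigates the effectiveness of the VR training system on situation awareness".

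**The concern.** One primary question with three answers and no rule for combining them leaves room for choice after the data are seen. The same three p-values could be written up as VR improving learning, as a mixed result, or as nothing shown. If one significant outcome out of three were enough, the chance of a false positive answer would exceed that of a single test.

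The wording on purpose does not settle whether the tests explore or are meant to support a claim. The Data Analysis section also pairs attitudes with self-confidence, whereas the Study Aims section names self-confidence alone. The analysed score could therefore be the 8-item subscale, the 13-item total, or two separate scores, which would make four tests.

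**Working it through.** **1. Does the plan's sample size supply a test level?** Inputs from the Participants section: margin of error 0.05, 95% confidence, p = 0.5, 200 eligible students.

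- Formula as printed: 1.96² × 0.5 × 0.5 / 0.05² = 384.1, so 385.
- With a finite population correction, which the plan does not mention: 384.1 / (1 + 383.1/200) = 131.7, so 132. This reproduces the plan's figure.
- 132/150 = 0.88, an implied 12% dropout allowance.

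This is a one-sample precision calculation. It contains no power, effect size or two-group test, so the 5% in it is not a test level.

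**2. Error rate under each reading.** Assumptions not in the plan: two-sided 5% per test, normal test statistics, no true effect, and groups that differ only by chance. With independent outcomes:

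- each outcome answered separately: 2.5% favouring VR for each;
- any one suffices: 1 − 0.975³ = 7.3% favouring VR (1 − 0.95³ = 14.3% in either direction);
- all three required: 0.025³ = 0.002%.

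With equally correlated outcomes, chance of a false result favouring VR:

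| Correlation | Any one suffices | All three required |
|---|---|---|
| 0 | 7.3% | 0.002% |
| 0.5 | 6.3% | 0.2% |
| 0.7 | 5.5% | 0.4% |
| 0.8 | 4.9% | 0.7% |
| 0.9 | 4.2% | 1.1% |

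Only the middle column exceeds 2.5%. If satisfaction were tested as a fourth outcome, the independent figure for that column would be 1 − 0.975⁴ = 9.6%.

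**3. Which reading does the text support?** The aims number the outcomes, the Instrumentation section treats them as three dependent variables, and the Data Analysis section tests variables, not a composite. No section says that one significant result answers the question for all three. The text reads most naturally as three separate comparisons. The sentences on purpose in the Study Aims section and the Conclusion are ordinary descriptions, and neither commits the study to an overall claim.

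**4. What would Holm cost?** Assumptions: 132 completers split 66/66, 80% power, Mann-Whitney efficiency 3/π. The detectable difference is (z for the test level + 0.842) × √(2 / (66 × 3/π)), and the square root is 0.178.

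- At 5%: (1.960 + 0.842) × 0.178 = 0.50 SD.
- At 5%/3 = 1.67%, Holm's strictest step: (2.394 + 0.842) × 0.178 = 0.58 SD.

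If all three outcomes truly differ by 0.50 SD, average power per outcome falls from 80.2% to 75.2% (correlation 0) or 71.7% (correlation 0.9), a loss of 5.0 to 8.5 points. Holm would hold the any-one rate to 2.5% at correlation 0 and 1.5% at 0.9.

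A larger sample could buy this back. Keeping 0.50 SD at the strictest step needs 132 × (0.576/0.499)² = 176 completers, or 176 × 150/132 = 200 recruits, the whole eligible pool. That applies when only one outcome truly differs. If all three do, about 146 completers (correlation 0) to 158 (correlation 0.9) restore 80% average power, or 166 to 180 recruits at the same allowance.

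**5. The score name.** The Instrumentation section itself uses the word attitudes for what the whole 13-item inventory assesses, so the phrase in the Data Analysis section is shorthand for that inventory. Its scoring sentence treats the two subscales apart: "Scores are calculated by summing responses; higher scores indicate more satisfaction and more self-confidence, respectively". Together with an aim that names self-confidence alone, this identifies the 8-item sum as the third outcome.

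**The case for a change.** The strongest opposing case does not depend on the size of the inflation. A primary question should have its decision rule written before results are seen, and nothing here stops someone from headlining whichever outcome is significant. Writing the rule down would take a few sentences, and declaring the tests exploratory would cost no power.

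Most of the factual part stands: test level, sidedness and combination rule are all absent, and stating them would make the plan clearer. What does not stand is the step from missing detail to error. The harm needs a reading that no section adopts, and both separate reporting and an all-three rule leave the error rate of the claim uninflated. Whether to adjust across distinct outcomes that are each reported is a matter on which statisticians differ. Labelling the tests exploratory would record a policy without altering any analysis.

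Holm also does not reach the larger threat to an effectiveness statement: "Two intact groups, which cannot be randomly assigned, serve as the control and intervention groups". An outcome that passed Holm would show a difference between two intact groups, which is not by itself an effect of VR.

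**Conclusion.** The concern describes the documents correctly but does not call for a change. The plan leaves unwritten a convention that analysts can fill sensibly: two-sided 5% for each outcome, all three between-group differences reported with 95% confidence intervals, and no overall claim resting on one significant outcome. On that reading the false-positive rate is 2.5% per outcome in favour of VR. The rise to between 4.2% and 7.3% arises only if any single outcome is allowed to answer for all three. Guarding against that with Holm would cost 5 to 8.5 points of average power, a fair trade-off to decline.

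These figures assume 5% tests, normal statistics, 66 completers per group and a 0.50 SD difference, none of which the plan states. They also leave out bias from non-random groups. The score name is a clerical matter that the Instrumentation section settles. The judgement would change if a report drew a general conclusion that VR improves learning from one significant result among three.

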## **Methodology**

### Study design

The study employs a quasi-experimental, pretest-posttest non-equivalent waitlist control group design. It is unethical to forbid a group of students from receiving a potential beneficial educational intervention for their learning purposes. In contrast, a waitlist design is appropriate to address the concern. The control group will not receive the intervention until after data has been collected. A pretest-posttest method will be used because of possible differences between the two groups.

Two intact groups, which cannot be randomly assigned, serve as the control and intervention groups. The intervention group will be having the VR training, whereas the control group will not until the study is completed.

## Participants

Students studying Bachelor of Science in Nursing who have completed the subject “Clinical reasoning and decision making in action part 1” are eligible to participate in the study (n=200). The researcher accepts a margin of error at 5%, confidence interval at 95% and standard deviation of 0.5. By using the Z-score formula (*Necessary Sample Size = (Z-score)2 \* StdDev\*(1-StdDev) / (margin of error)2*), the sample size should be  $N = 132$ . To avoid dropout and attrition from the participants, the researcher will recruit 150 samples to participate in the study.

Convenience sampling will be adopted to recruit subjects. Participants will be assigned to two study groups, the control and the experimental group. The Control group will have usual teaching activities (simulation), whereas the participants of the intervention group, will have VR sessions.

[figure not shown]

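### The sample size rests on a survey formula for one percentage, with an unwritten finite-population step, and not on the planned two-group comparison of score changes

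*Combined protocol and SAP*

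**What the plan says.** The Participants section counts the students who have completed the prerequisite subject and "are eligible to participate in the study (n=200"). It then gives the inputs: "The researcher accepts a margin of error at 5%, confidence interval at 95% and standard deviation of 0.5". The formula printed there is the squared Z-score times StdDev × (1 − StdDev), divided by the squared margin of error, and the result is stated as N = 132. The step to the recruitment target is "To avoid dropout and attrition from the participants, the researcher will recruit 150 samples to participate in the study". No dropout rate is given. The same section says that recruitment is by convenience sampling.

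The study itself is a comparison. Study Aims asks whether VR improves three outcomes: "1) situation awareness; (2) communication skills; and (3) self-confidence in learning". Study design states "Two intact groups, which cannot be randomly assigned, serve as the control and intervention groups". Data Analysis states "Mann-Whitney U test will be used to examine the changes in mean scores of variables" between the control and experimental groups. Data Analysis also has a descriptive aim: means and medians "will describe the prevalence of attitudes and self-confidence, level of situation awareness and communication skills".

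**The concern.** There are two faults, and the second matters more.

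- **The printed formula and its answer disagree.** A reader who puts the stated inputs into the stated formula does not get 132.
- **The formula answers a different question.** It sets how precisely one percentage is estimated in one sample. The primary question concerns a difference between two groups in the change of a score. The input called a standard deviation enters as StdDev × (1 − StdDev), which makes it a proportion and not the SD of any score in the Instrumentation section.

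At stake is how the result can be read. A reader of the Participants section could think the study is accurate to 5%. The same reader cannot tell what difference in score change 150 students could detect, and so cannot judge what a null result would mean.

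**Working it through.** **Inputs from the Participants section:** margin 0.05; 95% confidence (z = 1.96, taken as two-sided because the sidedness is not stated); 0.5 entered as a proportion; 200 eligible; 132 stated; 150 to be recruited.

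**1. The formula as printed**

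n0 = 1.96² × 0.5 × 0.5 / 0.05² = 0.9604 / 0.0025 = 384.16, so 385. This is not 132.

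**2. Reproducing 132**

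With a finite-population correction for N = 200:

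n = n0 / (1 + (n0 − 1)/N) = 384.16 / (1 + 383.16/200) = 384.16 / 2.9158 = 131.75, so 132.

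The close variant n0 / (1 + n0/N) gives 131.5, which also rounds up to 132. A one-sided z of 1.645 gives 270.6 without the correction and 115.2 with it, so it does not reproduce the figure. The shortcut N / (1 + N × 0.05²) gives 133.3, which is close but not 132. A finite-population step is therefore the likely route, but the documents do not say which one was used.

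**3. What 132 then means**

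The margin for one percentage near 50%, from 132 students out of 200, is

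1.96 × √(0.25/132) × √((200 − 132)/199) = 0.0853 × 0.5846 = 0.0499, or 5 points.

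Without the correction it is 8.5 points. Either way it describes one percentage in one sample. A margin of this kind also presumes random sampling from the 200, whereas the plan uses convenience sampling.

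**4. The step to 150**

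132/150 = 0.88. The plan therefore implies a 12% loss (132/0.88 = 150), although it does not state a rate.

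**5. What these numbers can detect in the planned comparison**

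The documents do not give the inputs, so all of the following are assumed: equal groups, independent observations, two-sided alpha 0.05 for one outcome, 80% power, normal data, and Mann-Whitney efficiency 3/π = 0.955 relative to the t test. The simple approximation for n per group is

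d = (1.96 + 0.842) × √(2 / (0.955 n)).

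- n = 75 (150 evaluable): 2.802 × √(2/71.6) = 0.468 SD
- n = 66 (132 evaluable): 2.802 × √(2/63.0) = 0.499 SD

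Replacing the normal by the noncentral t distribution changes these only slightly:

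| Evaluable | Detectable at 80% power, equal groups | Detectable at 80% power, groups 1:2 | Power for 0.3 SD, equal groups |
|---|---|---|---|
| 150 | 0.471 SD | 0.500 SD | 43% |
| 132 | 0.503 SD | 0.533 SD | 39% |

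A simulation of the Mann-Whitney test itself on normal data (20,000 runs, 75 per group) gave 80.4% power at 0.471 SD and 42.5% at 0.3 SD, which agrees with the table.

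**6. Is there another basis in the documents?**

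No other section supplies an effect size, score SD, test alpha or power. The descriptive aim in Data Analysis uses the word prevalence but reports means and medians, so it is not the estimation of a percentage either. The flow diagram is not shown. It might hold group sizes, but group sizes alone would not link 132 to the comparison.

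**The case against.** The strongest defence is that the calculation is sound and only badly reported. The 200 is printed just before the formula, the correction is standard, and it reproduces 132. This stands as far as it goes: the gap between 385 and 132 is an omitted step, and it is the lesser of the two faults. It does not rescue the justification, because the completed calculation still concerns one percentage.

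A second defence is that 132 happens to be reasonable: under the assumptions above it gives about 80% power for half an SD. That is arithmetically right, but the protocol never sets that target, so the match is a coincidence.

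Two stronger readings are tempting, and the documents support neither.

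- **That the study needs 385 students.** Only 200 are eligible, and 385 answers the same wrong question without the correction.
- **That 132 or 150 is too small.** To show this one would need a difference the investigators regard as meaningful and the SD of the score change. The documents give neither.

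The detectable differences have limits of their own. They are for one outcome at alpha 0.05, while Study Aims names three. They assume normal data, although the self-confidence inventory sums five-point items and will produce ties. They also assume independent students and equal groups, although the groups are intact and the readable text gives no allocation ratio. These are reasons to label the assumptions, not to keep the survey formula.

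**Conclusion.** The concern holds as a fault of justification. The printed formula gives 385 and not 132. The 132 is recovered (131.75) only through a finite-population step that is unwritten and inferred. With that step supplied, the 5% margin still does not describe the precision or power of the between-group comparison that the study is built on.

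No shortfall is established. Under the labelled assumptions the plan's own numbers correspond to a moderate detectable difference of about 0.47 SD (150 evaluable) to 0.50 SD (132 evaluable), with less than an even chance of detecting 0.3 SD. Unequal groups or correlation within teaching sessions would enlarge the detectable difference. None of these figures addresses pre-existing differences between the two intact groups.

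The point should be fixed, since the stated basis is wrong as written and the correction is cheap. It gives no reason to change recruitment or analysis.

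**What to change.** In the Participants section, delete the survey formula, the 5% margin and the 0.5 standard deviation as the justification. Keep the recruitment target of 150 and the 132 evaluable students it allows for (12% loss), and state what they can detect. Possible wording:

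> We will recruit 150 students, which allows for 12% loss and leaves 132 evaluable. Assuming equal groups, independent observations, two-sided alpha 0.05 for one outcome and Mann-Whitney efficiency 0.955 (normal data), the study has 80% power for a between-group difference in score change of about 0.47 SD with 150 evaluable and about 0.50 SD with 132 evaluable. Power for 0.3 SD is about 43% and 39%. These values are calculated from the recruitment target and are not an effect chosen in advance. Unequal groups (for example 1:2: about 0.50 and 0.53 SD) or correlation within teaching sessions would make the detectable difference larger. Tied scores may change these figures, and they do not address differences between the two intact groups.

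The text should not say that 150 is limited by the number of eligible students. The plan derives it as 132 plus an allowance for dropout, and 200 are eligible. If the investigators have a score SD or a difference they regard as meaningful, adding it would let readers judge the SD figures.

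The cost is protocol wording: no extra students and no change of analysis. The downside is that a moderate detectable difference with open assumptions looks less favourable than a 5% margin.
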